### 3.6.3 Additional safety assessments

#### 3.6.3.1 *Laboratory variables and vital signs*

The following laboratory variables and vital signs variables will be analyzed. They will be converted into standard international units.

- Hematology:
  - Red blood cells and platelets: hemoglobin, hematocrit, platelet count
  - White blood cells: leukocytes, neutrophils, lymphocytes, monocytes, basophils, eosinophils
- Clinical chemistry:
  - Metabolism: glucose, albumin, lipase, amylase
  - Electrolytes: sodium, potassium, chloride, calcium corrected, bicarbonate, magnesium
  - Calcium Corrected (mmol/L) = Total calcium (mmol/L) + 0.8 \* 0.25 \* [4 – Serum albumin (g/L) \* 0.1]
  - Renal function: creatinine, eGFR, blood urea nitrogen
  - Liver function: alanine aminotransferase, aspartate aminotransferase, alkaline phosphatase, lactate dehydrogenase, bilirubin
  - Vital signs: heart rate, systolic and diastolic blood pressure, respiratory rate, temperature, ECOG Performance status

Data below the lower limit of quantitation/detection limit (LLOQ) will be replaced by half of the LLOQ, data above the upper limit of quantification will be replaced by ULOQ value.

For hematological parameters and some selected biochemistry parameters, Sanofi sponsor generic ranges (LLN, ULN) are defined and will be used for grading (see list of parameters in [Section 5.4](#)). For other biochemistry parameters, grading will be derived using local laboratory normal ranges.

## **Analyses according to PCSA and NCI grading**

For laboratory variables, analyses according to NCI grading will be made based on NCI-CTCAE version 5.0. In addition, for eGFR, blood urea nitrogen, hematocrit, monocytes, basophils and chloride, PCSA analyses will be performed based on the PCSA list currently in effect at Sanofi at the time of the database lock.

Analyses according to PCSA and NCI grading will be performed based on the worst value during the treatment-emergent period, using all measurements (either local or central, either scheduled, nonscheduled or repeated).

For laboratory variables and vital signs above, the incidence of participants with at least one PCSA during the treatment-emergent period will be summarized regardless of the baseline level and according to the following baseline status categories:

- Normal/missing
- Abnormal according to PCSA criterion or criteria

For laboratory variables graded by NCI-CTCAE,

- The number (%) of participants with abnormal laboratory tests at baseline will be presented by grade.
- The number (%) of participants with abnormal laboratory tests during the treatment-emergent period will be summarized by grade. When appropriate, the number (%) of participants with abnormality of any grade and with Grade 3-4 abnormalities will be provided.

## **3.7 OTHER ANALYSES**

### **3.7.1 Other variables and/or parameters**

#### **3.7.1.1 PK analyses**

PK parameters will include but may not be limited to those listed in [Table 11](#), depending on the IMP and type of PK. The intensive PK parameters will be calculated using non-compartmental method from SAR444245 concentrations.

**Table 11 - List of PK parameters and definitions**

Parameters	Definition	Intensive PK SAR444245	Sparse PK SAR444245	Sparse PK cetuximab
$C_{trough}$	Concentration observed just before intervention administration during repeated dosing			X
$C_{EOI}$	Concentration at end of infusion		X	X
$C_{max}$	Maximum concentration observed	X		

Parameters	Definition	Intensive PK SAR444245	Sparse PK SAR444245	Sparse PK cetuximab
$C_{last}$	Last concentration observed above the lower limit of quantification	X		
$t_{last}$	Time of the last concentration observed above the lower limit of quantification (ie, $C_{last}$ )	X		
$AUC_{last}$	Area under the plasma concentration versus time curve calculated using the trapezoidal method from time zero to $t_{last}$	X		
AUC	Area under the concentration versus time curve extrapolated to infinity	X		
$R_{ac}$	Observed accumulation ratio calculated using the following equation : $R_{ac} = \frac{AUC \text{ at Cycle 4 Day 1}}{AUC \text{ at Cycle 1 Day 1}}$	X		
$R_{ac,Cmax}$	Observed accumulation ratio calculated using the following equation : $R_{ac, Cmax} = \frac{Cmax \text{ at Cycle 4 Day 1}}{Cmax \text{ at Cycle 1 Day 1}}$	X		

These PK parameters will be summarized as indicated in following sections on the PK population. Sparse and intensive PK of SAR444245 will be analyzed separately.

All concentration values below the lower limit of quantitation (LLOQ) will be treated as zero in all summary statistics. Geometric mean will not be computed in case at least one concentration is below LLOQ.

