**Table 5 - Populations for analyses**

Population	Description
Screened	All participants who have given their informed consent.
Enrolled	All participants who have given their informed consent and have been allocated to an intervention (by IRT) regardless of whether the intervention was received or not.
Exposed	All participants who have given their informed consent and received at least one dose (even incomplete) of IMP (SAR444245 or other anticancer therapies).
Population without trial impact (disruption) due to COVID-19	All exposed participants: 

without any critical or major deviation related to COVID-19

and who did not permanently discontinue treatment due to COVID-19

and who did not permanently discontinue study due to COVID-19

Efficacy	All participants from the exposed population with at least one evaluable post-baseline tumor assessment or who permanently discontinued study treatment.
Response-evaluable	All participants from efficacy population with an evaluable baseline and at least one evaluable post-baseline tumor assessments. Participants who died from disease progression before any TA will also be response-evaluable.
Pharmacokinetic (PK)	All participants from exposed population with at least 1 PK concentration available after the first dose of study intervention.
ADA	All participants from exposed population with at least 1 ADA result (positive, negative or inconclusive) after the first dose of study intervention.
Pharmacodynamics (PDy)	All participants from the exposed population with at least 1 PDy parameter assessed after the first dose of study intervention.

Participants exposed to study intervention before or without being enrolled will not be considered enrolled and will not be included in any analysis population. The safety experience of these participants will be reported separately.

For any participant enrolled and treated more than once, only the data associated with the first enrollment will be used in any analysis population. The safety experience associated with any later enrollment will be reported separately

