### **3.6.1.2 SAR444245 exposure**

The dose information will be assessed by the following:

- Total number of cycles started per participant
- Duration of SAR444245 exposure (in months) is defined by (date of last administration of SAR444245 + 21 – date of first administration of SAR444245)/30.4375.
- Actual dose ( $\mu\text{g}/\text{kg}$ )
- Cumulative dose ( $\mu\text{g}/\text{kg}$ ): the cumulative dose is the sum of all actual doses of SAR444245, given from first to last administration
- Actual dose intensity (ADI in  $\mu\text{g}/\text{kg}/\text{week}$ ): defined as the cumulative dose divided by the duration of SAR444245 exposure (in weeks)
- Planned dose intensity (PDI in  $\mu\text{g}/\text{kg}/\text{week}$ ): corresponds to the planned dose at C1D1 divided by the theoretical cycle duration expressed in weeks (i.e. 3 weeks)
- Relative dose intensity (RDI, in %):  $100 \times \frac{\text{ADI } (\mu\text{g}/\text{kg}/\text{week})}{\text{PDI } (\mu\text{g}/\text{kg}/\text{week})}$

The total number of cycles started, number of cycles started by participant will be summarized by category. Duration of SAR444245 exposure, cumulative dose, ADI and RDI will be summarized quantitatively and by category if relevant.

The following variables will be derived to describe dose modifications and dose interruptions:

- Dose reduction: The first administration will not be counted as a dose reduction. For the second and subsequent SAR444245 administrations, dose reduction will be determined using the dose level intervals provided in [Table 7](#), by comparing the current dose level to the previous dose level. If the current dose level is below the dose level interval of the previous dose administration, then the current dose level is considered reduced.

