**Table 7 - SAR444245 dose reduction criteria**

Actual dose level	Dose level interval
8 µg/kg	
16 µg/kg	
24 µg/kg	

- Dose omission is defined as a dose not administered at the scheduled visit.
- Dose interruption: A dose will be considered as interrupted if SAR444245 administration is stopped during an infusion regardless of whether it is restarted or not.

Dose modifications and dose interruptions will be analyzed by participant and dose as follows:

- **Participant** (number of participants treated will be used as denominator)
  - Number (%) of participants with at least 1 dose modification
    - Number (%) of participants with at least 1 dose reduction
    - Number (%) of participants with at least 1 dose omission
  - Number (%) of participants with at least 1 dose interruption
    - Number (%) of participants with at least 1 dose interrupted and restarted
    - Number (%) of participants with at least 1 dose interrupted and not restarted
  - Number (%) of participants with at least 2 dose interruptions
- **Dose** (number of doses started will be used as denominator)
  - Number of doses
  - Number (%) of dose interruptions
  - Number (%) of doses interrupted and re-started
  - Number (%) of doses interrupted and not re-started
  - Number (%) of doses interrupted more than once,
  - Number (%) of doses interrupted at 1st dose, 2nd dose, subsequent doses,
  - Time from dose start to first interruption in minutes summarized as a continuous variable and by category.

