#### 3.7.1.1.1 Descriptive statistics

The PK variables defined above will be summarized by cycle separate for Chinese and non-Chinese subjects, as well as pooling all subjects, using the following descriptive statistics: mean, median, standard deviation, coefficient of variation, minimum, and maximum. In addition, geometric mean and geometric standard deviation will be calculated for concentration parameters. These analyses will be performed by specific subgroups (eg, gender, BMI, age) if appropriate.

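### The Cycle 4 / Cycle 1 accumulation ratios in Table 11 have no dose term, so in participants whose SAR444245 dose was reduced they mix dose change with accumulation

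*SAP*

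**What the plan says.** SAP Section 3.7.1.1, Table 11, lists Rac and Rac,Cmax among the intensive PK parameters of SAR444245. Each is called an "Observed accumulation ratio calculated using the following equation". The equations divide AUC at Cycle 4 Day 1 by AUC at Cycle 1 Day 1, and Cmax at Cycle 4 Day 1 by Cmax at Cycle 1 Day 1. Neither contains the dose.

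SAP Section 3.6.1.2 expects the dose to change in some participants: "For the second and subsequent SAR444245 administrations, dose reduction will be determined using the dose level intervals provided in" Table 7, which lists 8, 16 and 24 µg/kg. The planned output includes "Number (%) of participants with at least 1 dose reduction". The same section lists the actual dose in µg/kg as an exposure variable.

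The PK population in Table 5 is "All participants from exposed population with at least 1 PK concentration available after the first dose of study intervention". It sets no condition on dose.

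Section 3.7.1.1.1 then states: "The PK variables defined above will be summarized by cycle", separately for Chinese and non-Chinese subjects and pooled. Further subgroups are allowed where appropriate, with gender, BMI and age as examples. Dose received is not named.

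**The concern.** A ratio of two exposures measures accumulation only if the two doses were equal, or if each exposure is scaled by its own dose. The SAP requires neither, yet it plans to derive and count reductions that can fall between the two visits. For a participant reduced in between, the parameter combines accumulation and the dose change in one number, and the reported value gives no means of separating them.

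PK parameters of SAR444245 are a secondary endpoint (SAP Table 2). Section 3.7.1.2 also allows the impact of a positive immune response on PK to be explored. Lower Cycle 4 exposure after a reduction would look the same in these ratios as lower exposure from anti-drug antibodies. The Cycle 4 summaries of AUC, Cmax and C_EOI can mix dose levels for the same reason.

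**Working it through.** The SAP states no numerical accumulation ratio, so there is no figure to reproduce. The check asks what the formula returns when the dose changes.

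**Inputs from the SAP**
- Ratio: Cycle 4 Day 1 exposure over Cycle 1 Day 1 exposure (Table 11).
- Dose levels: 8, 16 and 24 µg/kg (Table 7).
- Reductions possible from the second administration (Section 3.6.1.2).

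**Inputs the SAP does not give, taken as assumptions**
- Exposure is proportional to dose.
- True accumulation at constant dose: 1.0 to 2.0.
- Share of participants with both intensive PK visits who are reduced by Cycle 4: 10% to 50%.
- Path of the reduction: each pair of Table 7 levels is shown, because the SAP text does not state the starting dose.

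**Step 1: one participant.** Observed ratio = true ratio × (dose at Cycle 4 / dose at Cycle 1).

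| Change (µg/kg) | Factor | True 1.0 | True 1.5 | True 2.0 |
|---|---|---|---|---|
| 24 to 16 | 16/24 = 0.67 | 0.67 | 1.00 | 1.33 |
| 16 to 8 | 8/16 = 0.50 | 0.50 | 0.75 | 1.00 |
| 24 to 8 | 8/24 = 0.33 | 0.33 | 0.50 | 0.67 |

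Under proportionality, accumulation of 1.5 with a step from 24 to 16 is reported as 1.00.

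**Step 2: the mean over participants.** With share f reduced by dose factor r, and the same true ratio in everyone, the mean is multiplied by (1 − f) + f × r.

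| Share reduced | 24 to 16 | 24 to 8 |
|---|---|---|
| 10% | 0.90 + 0.10 × 0.667 = 0.97 | 0.90 + 0.10 × 0.333 = 0.93 |
| 25% | 0.75 + 0.25 × 0.667 = 0.92 | 0.75 + 0.25 × 0.333 = 0.83 |
| 50% | 0.50 + 0.50 × 0.667 = 0.83 | 0.50 + 0.50 × 0.333 = 0.67 |

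**Step 3: after the change.** In participants with equal doses the factor is 1, so the true ratio is returned with no assumption about proportionality. With dose normalisation, (AUC at Cycle 4 / dose at Cycle 4) divided by (AUC at Cycle 1 / dose at Cycle 1) also returns the true ratio, but only if exposure is proportional to dose.

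**The case against.** The strongest reply is that Table 11 calls the ratio observed, and an observed ratio is what it delivers. It is descriptive, and no test, decision rule or dose choice in the SAP uses it. Section 3.7.1.1 leaves the parameter list open and Section 3.7.1.1.1 gives its subgroups only as examples, so a dose-normalised ratio or a split by dose could be added without departing from the plan. This is permission and not a specification: the formula that is fixed remains the raw one.

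A reader might infer that the SAP will take a low ratio in a reduced participant as absence of accumulation. It does not say how Rac will be interpreted, and dose reductions are reported elsewhere, although not linked to each ratio. A reader might also infer that PK is summarised by cycle alone. It is not, given the Chinese / non-Chinese split and the optional subgroups. Nor must the distortion always be downward: the reductions lower the ratio, but an incomplete Cycle 1 infusion would raise it.

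The size is also open to challenge. Proportionality, the dose path and the share reduced all lack a source in the SAP. The figures concern the mean, whereas the median is planned too. In the simple model above, with a common true ratio, the median does not move when fewer than half are reduced, and a low minimum would be visible. Finally, dividing by dose relies on the same unproven proportionality. These objections stand, and they limit the claim and shape the fix. They do not make the raw ratio a clean measure of accumulation when doses differ.

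**Conclusion.** The point holds as a minor one. Followed as written, Table 11 returns a number that mixes dose change with accumulation in every participant whose dose differs between Cycle 1 Day 1 and Cycle 4 Day 1, and no other part of the SAP removes or separates these participants. That much rests on the text alone.

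The size rests on assumptions. Under dose proportionality the individual ratio is scaled by 0.67, 0.50 or 0.33. The effect on the mean ranges from slight, at 0.97 with 10% reduced from 24 to 16, to substantial, at 0.67 with 50% reduced from 24 to 8. The documents do not show which of these is closer, or that any participant with intensive PK at both visits will have been reduced.

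Only participants with intensive PK at both visits and a changed dose contribute to the distortion of the ratios. The primary ORR analysis and the safety analyses are untouched.

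**What to change.** In Table 11, define Rac and Rac,Cmax for participants with the same actual SAR444245 dose level at Cycle 1 Day 1 and Cycle 4 Day 1, and report how many are left out because the dose changed. Add a supportive version in all participants with both visits, using AUC and Cmax divided by the actual dose of that administration, with a note that it assumes dose proportionality. In Section 3.7.1.1.1, present Cycle 4 AUC, Cmax and C_EOI by actual dose level in addition to the splits already planned.

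The cost is a line or two in Table 11, one by-variable and one extra table. No new data are needed, because the actual dose is already derived under Section 3.6.1.2. The restricted ratio will include slightly fewer participants and describes only those whose dose was unchanged, which is why the supportive version is worth keeping. Dosing and the rules for dose reduction are not affected.

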#### 3.7.1.1.1 Descriptive statistics

The PK variables defined above will be summarized by cycle separate for Chinese and non-Chinese subjects, as well as pooling all subjects, using the following descriptive statistics: mean, median, standard deviation, coefficient of variation, minimum, and maximum. In addition, geometric mean and geometric standard deviation will be calculated for concentration parameters. These analyses will be performed by specific subgroups (eg, gender, BMI, age) if appropriate.

#### 3.7.1.2 Immunogenicity analyses

Participant's ADA status, response variable and kinetics of ADA responses (see definitions below) will be summarized on the ADA population.

Kinetics of ADA responses will be described for participants with treatment-induced ADA and for participants with treatment-boosted ADA, separately. Time to ADA onset and duration of ADA will be described with minimum, Q1, median, Q3 and maximum statistics.

Peak titer will be described with minimum, Q1, median, Q3 and maximum statistics for participants with treatment-induced ADA and for participants with treatment-boosted ADA, separately.

ADAs against SAR444245 (negative, positive, inconclusive) and corresponding titers, ADAs directed against PEG moiety of SAR444245 status (negative, positive) and ADAs cross-reacting with endogenous IL-2 status (negative, positive) will also be described overtime using descriptive statistics. ADAs directed against PEG moiety of SAR444245 status and ADAs cross-reacting with endogenous IL-2 status will only be determined if the status of ADAs against SAR444245 is positive.

The impact of positive immune response on efficacy, PK and safety variables may be further explored, depending on ADA incidence.

#### **Participant's ADA status against SAR444245**

- Participants with **pre-existing ADAs** correspond to participants with ADAs present in samples drawn before first administration of intervention. Participants with missing ADA sample at baseline will be considered as without pre-existing ADA.
- Participants with **treatment-emergent ADA** correspond to participants with at least one treatment-induced/boosted ADA.
  - Participants with **treatment-induced ADAs** correspond to participants with ADAs that developed during the treatment-emergent (TE) period and without pre-existing ADA (including participants without pre-treatment samples).
  - Participants with **treatment-boosted ADAs** correspond to participants with pre-existing ADAs that are boosted during the TE period to a significant higher titer than the baseline. A 2-fold serial dilution schema is used during titration, so at least a 4-fold increase will be considered as significant.
- Participants with **unclassified ADA** correspond to participants with pre-existing ADAs that cannot be classified as treatment-boosted ADA because of missing titer(s) (ie, a positive ADA sample during the TE period in a participant with pre-existing ADA but with missing titer at this sample or at baseline).
- Participants **without treatment-emergent ADA** correspond to participants without treatment-induced/boosted ADA and without any inconclusive sample nor unclassified ADA during the TE period.
- Participants **with inconclusive ADA** are defined as participants which cannot irrefutably be classified as with or without treatment-emergent ADA.

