**ADA response variable:**

- **ADA incidence** is defined as the proportion of participants found to have seroconverted (treatment-induced ADAs) or boosted their pre-existing ADA response (treatment-boosted ADAs) at any time point during the TE period.
- **Incidence of ADAs** directed against PEG moiety of SAR444245 is defined as the proportion of participants with ADAs directed against PEG moiety of SAR444245 during the TE period among evaluable participants. Participants from ADA population are evaluable for ADAs directed against PEG moiety except if ADAs directed against PEG moiety status is not determined on an ADA against SAR444245 positive sample
- **Incidence of ADAs cross-reacting with endogenous IL-2** is defined as the proportion of participants with ADAs directed against endogenous IL-2 during the TE period among evaluable participants. Participants from ADA population are evaluable for ADAs directed against endogenous IL-2 except if their status is not determined on an ADA against SAR444245 positive sample.

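### Counting a missing baseline ADA sample as negative can only understate pre-existing ADA prevalence, and it mixes positives of unknown origin into treatment-induced ADA

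*SAP*

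**What the plan says.** SAP section 3.7.1.2, under the heading on participant ADA status, gives the rule for an absent baseline: "Participants with missing ADA sample at baseline will be considered as without pre-existing ADA". The definition of treatment-induced ADA in the same list repeats the choice, covering people with no pre-existing ADA and "including participants without pre-treatment samples".

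Table 5 defines the ADA population as exposed participants "with at least 1 ADA result (positive, negative or inconclusive) after the first dose of study intervention". No baseline sample is required. Section 3.7.1.2 states that ADA status, the response variable and the kinetics "will be summarized on the ADA population".

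ADA incidence, a secondary endpoint in Table 2, counts treatment-induced plus treatment-boosted participants. A participant with known pre-existing ADA counts as boosted only after at least a 4-fold titer rise. Time to onset and peak titer are described separately for the induced and boosted groups. The SAP plans no count of missing baseline samples and no sensitivity analysis for them.

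**The concern.** Without a baseline sample, an on-treatment positive cannot be dated. It may be new, or it may have been present before the first dose. The SAP resolves the doubt by setting the baseline to negative, and this affects two summaries differently.

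For pre-existing ADA, people who were never tested sit in the denominator and can never enter the numerator, so the reported prevalence is pulled down.

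For treatment-emergent ADA, the threshold for counting a case depends on whether the baseline sample exists. A known carrier needs the 4-fold rise. A carrier whose baseline sample is missing counts on any positive. An unchanged pre-existing antibody can therefore appear as treatment-induced, with an onset time that is really the time of the first on-treatment sample. The onset summaries use minimum, quartiles and maximum on the ADA-positive subset of cohorts of about 40, so the extremes in particular could move with one such participant.

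What is at stake is the reading of a descriptive immunogenicity table. As planned, it would not show how many treatment-induced cases are of unknown origin.

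**Working it through.** **Plan's own figure.** The SAP states no ADA prevalence, ADA incidence or missing-baseline rate, so there is nothing to reproduce. The only documented input is the scale of about 40 participants per cohort (section 4). All other values below are assumptions.

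**Assumed inputs**
- m: share of the ADA population without a baseline sample, 5% to 20%.
- p: true pre-existing prevalence, 2% to 20%, the same in those with and without a baseline sample.
- q: probability that a carrier tests positive on treatment, set to 1 (the worst case).
- b: probability that a carrier is truly boosted, set to 0.2.

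**Step 1: pre-existing prevalence.** Only the tested share (1-m) can contribute positives, while the denominator is everyone. Reported prevalence = p(1-m).

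| True p | m = 5% | m = 10% | m = 20% |
|---|---|---|---|
| 10% | 9.5% | 9.0% | 8.0% |
| 20% | 19% | 18% | 16% |

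For example, 0.20 × (1 - 0.10) = 0.18. The direction does not depend on the missingness mechanism. If prevalence among the untested is p', the full-population value exceeds the reported one by m × p', which is never negative.

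**Step 2: treatment-induced ADA.** Carriers without a baseline who test positive on treatment are added to the induced group. Excess = m × p × q.
- m = 5%, p = 2%: 0.05 × 0.02 × 1 = 0.1 percentage point, or 0.04 of 40 participants.
- m = 10%, p = 10%: 0.10 × 0.10 × 1 = 1.0 point, or 0.4 of 40.
- m = 20%, p = 20%: 0.20 × 0.20 × 1 = 4.0 points, or 1.6 of 40.

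**Step 3: total ADA incidence.** Carriers who are truly boosted would have counted in any case, so the net excess is smaller: m × p × (q - b).
- m = 10%, p = 10%: 0.10 × 0.10 × 0.8 = 0.8 point, or about 0.3 of 40.
- m = 20%, p = 20%: 0.20 × 0.20 × 0.8 = 3.2 points, or about 1.3 of 40.

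Because q cannot exceed 1 and b cannot fall below 0, the excess in total incidence is at most m × p. With m = 0, every effect above is zero.

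**The case against.** The strongest reply is that the rule is deliberate, written down in advance and cautious. Section 3.7.1.2 assigns these participants expressly, in two places. The default attributes doubtful antibodies to the drug, so it does not understate ADA incidence, which is the secondary endpoint. It matches other defaults in section 3.6.2, where an adverse event with an incomplete onset date is normally taken as treatment-emergent and one with a missing relationship as related. Pre-existing prevalence is not a named endpoint, no formal testing is done (section 3.5), and the effect may be nil. Section 3.7.1.2 also describes ADA results over time. If baseline is among the time points shown, which the SAP does not say, that display would give positivity among samples actually taken.

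Most of this stands. It does not rescue the prevalence figure: a default that is cautious for incidence understates prevalence.

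A reader might also infer that the SAP contradicts itself. The text does not support that, for three reasons:
- The unclassified category is confined to participants with known pre-existing ADA and a missing titer, so it does not reach someone with no baseline sample. The two defaults address different missing items: in one the 4-fold criterion cannot be computed, in the other the baseline status itself is absent.
- The inconclusive category covers "participants which cannot irrefutably be classified as with or without treatment-emergent ADA". That wording is loose, and taken alone it could seem to describe a positive participant with no baseline. But the treatment-induced definition already classifies that participant, so nothing is left for the residual category.
- The incidence definition speaks of seroconversion but ties the word in parentheses to treatment-induced ADA as defined, which includes participants without a pre-treatment sample.

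**Conclusion.** The point holds as a small matter of estimation and transparency. Pre-existing ADA prevalence is understated whenever baselines are missing among carriers. The treatment-induced group and its time to onset can absorb antibodies that predate treatment. Counting no-baseline positives in overall incidence is an acceptable conservative convention.

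It would go too far to say that the reported figures will be wrong. The SAP gives no missing-baseline rate, and complete baseline sampling removes the issue. On the assumed ranges, the induced group gains between 0.04 and 1.6 participants per cohort of 40, and total incidence gains less. These sizes rest on equal prevalence in tested and untested participants, and on every carrier testing positive on treatment. The downward direction for prevalence needs neither assumption. This is a cheap improvement in a descriptive analysis and does not threaten the trial's conclusions.

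**What to change.** In section 3.7.1.2:
1. Compute pre-existing ADA prevalence over participants with a baseline ADA result, and report how many in the ADA population have none. This returns the estimate from p(1-m) to p if missingness is unrelated to carrier status.
2. Keep the conservative overall ADA incidence, but show on-treatment positives without a baseline sample as a separate row within treatment-induced ADA.
3. Also give ADA incidence and time to onset restricted to participants with a baseline result.

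The SAP already uses evaluable-participant denominators for antibodies to the PEG moiety and for those cross-reacting with endogenous IL-2, so the approach is not foreign to it. The cost is a wording change, one extra row, the restricted summaries and a slightly smaller denominator for them. No new data are needed.
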